11.2. Institutional Review Board/Independent Ethics Committee

A copy of the protocol, proposed informed consent form, other written patient information, and any proposed advertising material must be submitted to the IRB for written approval. A copy of the written approval of the protocol and informed consent form must be received by AADI before recruitment of patients into the study and shipment of AADI IP.

The investigator must submit and, where necessary, obtain approval from the IRB for all subsequent protocol amendments and changes to the informed consent document. The investigator is to notify the IRB of deviations from the protocol or SAEs occurring at the site and other AE reports received from AADI, in accordance with local procedures.

The investigator is responsible for obtaining annual IRB approval [IRBs only]/renewal [IRBs and IECs] throughout the duration of the study. Copies of the investigator's reports and the IRB continuance of approval must be sent to AADI.

11.3. Patient Confidentiality

The investigator must ensure that the patient's confidentiality is maintained for documents submitted to AADI.

- Patients are to be identified by a unique patient identification number.
- Where permitted, date of birth is to be documented and formatted in accordance with local laws and regulations.
- On the CRF demographics page, in addition to the unique patient identification number, include the age at time of enrollment.
- For SAEs reported to AADI, patients are to be identified by their unique patient identification number, initials (for faxed reports, in accordance with local laws and regulations), and date of birth (in accordance with local laws and regulations).
- Documents that are not submitted to AADI (eg, signed informed consent forms) are to be kept in confidence by the investigator, except as described below.

In compliance with Federal regulations/ICH GCP Guidelines, it is required that the investigator and institution permit authorized representatives of the company, of the regulatory agency(s), and the IRB direct access to review the patient's original medical records for verification of study-related procedures and data. Direct access includes examining, analyzing, verifying, and reproducing any records and reports that are important to the evaluation of the study. The investigator is obligated to inform and obtain the consent of the patient to permit such individuals to have access to his/her study-related records, including personal information.

11.4. Protocol Amendments

If investigator amends the protocol, agreement from AADI must be obtained. The IRB must be informed of all amendments and give approval. The investigator must send a copy of the approval letter from the IRB to AADI.

11.5. Termination of the Study

Both AADI and the investigator reserve the right to terminate the Investigator's participation in the study according to the study contract. The investigator is to notify the IRB in writing of the study's completion or early termination and send a copy of the notification to AADI.

12. DATA HANDLING AND RECORDKEEPING

12.1. Data/Documents

The investigator must ensure that the records and documents pertaining to the conduct of the study and the distribution of the investigational product are complete, accurate, filed, and retained. Examples of source documents include: hospital records; clinic and office charts; laboratory notes; memoranda; checklists; dispensing records; recorded data from automated instruments; copies or transcriptions certified after verification as being accurate copies; microfiche; x-ray film and reports; and records kept at the pharmacy; and the laboratories, as well as copies of CRFs or CD-ROM.

12.2. Data Management

Data will be collected via CRF and entered into the clinical database. These data will be electronically verified through use of programmed edit checks specified by the clinical team. Discrepancies in the data will be brought to the attention of the clinical team, and investigational site personnel, if necessary. Resolutions to these issues will be reflected in the database. An audit trail within the system will track all changes made to the data.

12.3. Investigator Responsibilities for Data Collection

The investigator is responsible for complying with the requirements for all assessments and data collection (including patients not receiving protocol-required therapies) as stipulated in the protocol for each patient in the study. For patients who withdraw prior to completion of all protocol-required visits and are unable or unwilling to continue the Schedule of Assessments (Table 2), the investigator can search publically available records (where permitted) to ascertain survival status.

This ensures that the data set(s) produced as an outcome of the study is/are as comprehensive as possible.

12.4 Research Use of Fresh and Stored Human Samples, Specimens or Data

- Intended Use: Samples and data collected under this protocol will be used to study the effects of combination therapy with ABI-009, an mTOR inhibitor that affects the differentiation of M1 and M2 macrophages in the tumor microenvironment (TME), and a immune checkpoint inhibitor, nivolumab, that inhibits CTLA4 and PD-1 and ligands in the TME. No genetic testing will be conducted.
- Resected or biopsied tumors that are \geq than 500 mm³ will be collected and cut into two pieces. One piece of tumor will be placed in media, processed and analyzed by flow cytometry (FACS). The second piece will be placed in 10% neutral-buffered formalin and later processed to formalin-fixed paraffin-embedded (FFPE) blocks. Tumors that are \leq 500 mm³ in volume will be not be cut and the whole tumor will be used for FACS analysis.
- For biomarker studies, flow cytometry analysis will be for human CD45, CD3, CD4, CD8, CD56, LAG-3, PD-1 and PD-L1 markers. Cell suspensions will be divided in two tubes, and each tube will be analyzed independently for the individual set of markers. Tube 1: CD45, CD3, CD4, CD8, CD56, PD-1, PD-L1, viability. Tube 2:

CD45, CD3, CD4, CD8, CD56, LAG-3, CD19 or CD20 (B cell marker), TIM3, 4-IBB, and FoxP3 regulatory T cells.

- Histopathologic examination of resected or biopsied tumors will be conducted, the degree of tumor necrosis and mitotic index will be assessed, and immunohistochemical analysis for expression of PD-1, PD-L1, CD8+, CD4+, CD19, CD20, CD45, NK, Ki67, cyclin G1, cyclin D1 will be conducted.
- Storage: Access to stored samples will be limited using a locked freezer. Samples and data will be stored using codes assigned by the investigators. Data will be kept in password-protected computers. Only investigators will have access to the samples and data.
- Tracking: Data will be tracked using a secure database system (e.g. Merge eCOS).
- Disposition at the completion of the study: All stored samples will be archived at the clinical site. Study participants who request destruction of samples will be notified of compliance with such request and all supporting details will be maintained for tracking.

12.5 Future Use of Stored Specimens

All samples and associated results will be no less than single coded prior to being shipped from the site for analysis, or storage. Tracking of samples will be independent of the patient's identification number for the study. Data collected for this study will be analyzed and stored at the clinical site. After the study is completed, the de-identified, archived data will be transmitted to and stored in a secure database under the supervision of the principal investigator, for use by other researchers including those outside of the study. Permission to transmit data to the secure data base will be included in the informed consent.

The patient retains the right to request that the sample material be destroyed by contacting the Investigator. Following the request from the patient, the investigator is to provide the sponsor with the required study and patient number so that any remaining blood or tumor samples and any other components from the cells can be located and destroyed. Samples will be destroyed once all protocol-defined procedures are completed.

The sponsor is the exclusive owner of any data, discoveries, or derivative materials from the sample materials and is responsible for the destruction of the sample(s) at the request of the patient through the Investigator, at the end of the storage period, or as appropriate (e.g., the scientific rationale for experimentation with a certain sample type no longer justifies keeping the sample). The patient has no commercial rights to the products and has no commercial rights to the data, information, discoveries, or derivative materials gained or produced from the sample.

12.6 Sample Storage and Destruction

Any blood or tumor sample collected according to the Schedule of Assessments (Table 2) can be analyzed for any of the tests outlined in the protocol and for any tests necessary to minimize risks to study patients. This includes testing to ensure analytical methods

produce reliable and valid data throughout the course of the study. This can also include, but is not limited to, investigation of unexpected results, incurred sample reanalysis, and analyses for method transfer and comparability.

All samples and associated results will be no less than single coded prior to being shipped from the site for analysis, or storage. Tracking of samples will be independent of the patient's identification number for the study. Results are stored in a secure database to ensure confidentiality.

Results from this analysis are to be documented and maintained, but are not necessarily reported as part of this study.

The records should be retained by the Investigator/Sponsor according to ICH, local regulations, or as specified in the Clinical Trial Agreement, whichever is longer; but at a minimum, all study documentation must be retained for 2 years after the last marketing application approval in an ICH region or after at least 2 years have elapsed since formal discontinuation of clinical development of ABI-009.

Since the evaluations are not expected to benefit the patient directly or to alter the treatment course, the results of other exploratory studies are not placed in the patient's medical record and are not to be made available to the patient, members of the family, the personal physician, or other third parties, except as specified in the informed consent.

The patient retains the right to request that the sample material be destroyed by contacting the Investigator. Following the request from the patient, the investigator is to provide the sponsor with the required study and patient number so that any remaining blood or tumor samples and any other components from the cells can be located and destroyed. Samples will be destroyed once all protocol-defined procedures are completed.

The sponsor is the exclusive owner of any data, discoveries, or derivative materials from the sample materials and is responsible for the destruction of the sample(s) at the request of the patient through the Investigator, at the end of the storage period, or as appropriate (e.g., the scientific rationale for experimentation with a certain sample type no longer justifies keeping the sample). If a commercial product is developed from this research project, the sponsor owns the commercial product. The patient has no commercial rights to such product and has no commercial rights to the data, information, discoveries, or derivative materials gained or produced from the sample.

13. QUALITY CONTROL AND QUALITY ASSURANCE

13.1. Study Monitoring

The Institution representative, AADI representative(s) and regulatory authority inspectors are responsible for contacting and visiting the investigator for the purpose of inspecting the facilities and, upon request, inspecting the various records of the clinical study (eg, CRFs and other pertinent data) provided that patient confidentiality is respected.

The Institution representative together with the AADI representative are responsible for verifying the CRFs as needed throughout the study to verify adherence to the protocol; completeness, accuracy, and consistency of the data; and adherence to local regulations on the conduct of clinical research. Monitoring will include on-site visits with the investigator and his/her staff as well as any appropriate communications by mail, email, fax, or telephone. During monitoring visits, the facilities, IP storage area, CRFs, patient's source documents, and all other study documentation will be inspected/reviewed by the AADI representative in accordance with the Study Monitoring Plan.

The investigator agrees to cooperate with the clinical monitor to ensure that any problems detected in the course of these monitoring visits, including delays in completing CRFs, are resolved.

13.2. Audits and Inspections

In accordance with ICH GCP and the sponsor's audit plans, this study may be selected for audit by representatives from AADI's Inspection of site facilities (eg, pharmacy, protocol-required therapy storage areas, laboratories) and review of study-related records will occur to evaluate the study conduct and compliance with the protocol, ICH GCP, and applicable regulatory requirements.

14. PUBLICATIONS

The results of this study may be published in a medical publication, journal, or may be used for teaching purposes. Additionally, this study and its results may be submitted for inclusion in all appropriate health authority study registries, as well as publication on health authority study registry websites, as required by local health authority regulations. Selection of first authorship will be based on several considerations, including, but not limited to study participation, contribution to the protocol development, and analysis and input into the manuscript, related abstracts, and presentations in a study.

APPENDIX: ADVERSE EVENT MANAGEMENT ALGORITHMS FOR NIVOLUMAB

GI Adverse Event Management Algorithm

[figure not shown]
Rule out non-inflammatory causes. If non-inflammatory cause is identified, treat accordingly and continue I-O therapy. Opiates/narcotics may mask symptoms of perforation. Infliximab should not be used in cases of perforation or sepsis.

Patients on IV steroids may be switched to an equivalent dose of oral corticosteroids (e.g. prednisone) at start of tapering or earlier, once sustained clinical improvement is observed. Lower bioavailability of oral corticosteroids should be taken into account when switching to the equivalent dose of oral corticosteroids.

Renal Adverse Event Management Algorithm

[figure not shown]
Rule out non-inflammatory causes. If non-inflammatory cause, treat accordingly and continue I-O therapy

Patients on IV steroids may be switched to an equivalent dose of oral corticosteroids (e.g. prednisone) at start of tapering or earlier, once sustained clinical improvement is observed. Lower bioavailability of oral corticosteroids should be taken into account when switching to the equivalent dose of oral corticosteroids.

Pulmonary Adverse Event Management Algorithm

[figure not shown]
Rule out non-inflammatory causes. If non-inflammatory cause, treat accordingly and continue I-O therapy. Evaluate with imaging and pulmonary consultation.

Patients on IV steroids may be switched to an equivalent dose of oral corticosteroids (e.g. prednisone) at start of tapering or earlier, once sustained clinical improvement is observed. Lower bioavailability of oral corticosteroids should be taken into account when switching to the equivalent dose of oral corticosteroids.

Hepatic Adverse Event Management Algorithm

Rule out non-inflammatory causes. If non-inflammatory cause, treat accordingly and continue I-O therapy. Consider imaging for obstruction.

[figure not shown]
Patients on IV steroids may be switched to an equivalent dose of oral corticosteroids (e.g. prednisone) at start of tapering or earlier, once sustained clinical improvement is observed. Lower bioavailability of oral corticosteroids should be taken into account when switching to the equivalent dose of oral corticosteroids.

*I-O therapy may be delayed rather than discontinued if AST/ALT ≤ 8 x ULN or T.bili ≤ 5 x ULN.

**The recommended starting dose for grade 4 hepatitis is 2 mg/kg/day methylprednisolone IV.

Endocrinopathy Management Algorithm

[figure not shown]
Rule out non-inflammatory causes. If non-inflammatory cause, treat accordingly and continue I-O therapy. Consider visual field testing, endocrinology consultation, and imaging.

Patients on IV steroids may be switched to an equivalent dose of oral corticosteroids (e.g. prednisone) at start of tapering or earlier, once sustained clinical improvement is observed. Lower bioavailability of oral corticosteroids should be taken into account when switching to the equivalent dose of oral corticosteroids.

Skin Adverse Event Management Algorithm

Rule out non-inflammatory causes. If non-inflammatory cause, treat accordingly and continue I-O therapy.

[figure not shown]
Patients on IV steroids may be switched to an equivalent dose of oral corticosteroids (e.g. prednisone) at start of tapering or earlier, once sustained clinical improvement is observed. Lower bioavailability of oral corticosteroids should be taken into account when switching to the equivalent dose of oral corticosteroids.

*Refer to NCI CTCAE v4 for term-specific grading criteria.

**If SJS/TEN is suspected, withhold I-O therapy and refer patient for specialized care for assessment and treatment. If SJS or TEN is diagnosed, permanently discontinue I-O therapy.

Neurological Adverse Event Management Algorithm

Rule out non-inflammatory causes. If non-inflammatory cause, treat accordingly and continue I-O therapy.

Patients on IV steroids may be switched to an equivalent dose of oral corticosteroids (e.g. prednisone) at start of tapering or earlier, once sustained clinical improvement is observed. Lower bioavailability of oral corticosteroids should be taken into account when switching to the equivalent dose of oral corticosteroids.

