In Trial 1, there was an increased incidence of liver test abnormalities in the nivolumab-treated group as compared to the chemotherapy-treated group, with increases in AST (28% vs. 12%), alkaline phosphatase (22% vs. 13%), ALT (16% vs. 5%), and total bilirubin (9% vs. 0). Immune-mediated hepatitis, defined as requirement for corticosteroids and no clear alternate etiology, occurred in 1.1% (3/268) of patients receiving nivolumab: two patients with Grade 3 and one patient with Grade 2 hepatitis. The time to onset was 97, 113, and 86 days after initiation of nivolumab. In one patient, hepatitis was diagnosed after discontinuation of nivolumab for other reasons. In two patients, nivolumab was withheld. All three patients received high-dose corticosteroids (at least 40 mg prednisone equivalents). Liver tests improved to Grade 1 within 4-15 days of initiation of corticosteroids. Immune-mediated hepatitis resolved and did not recur with continuation of corticosteroids in two patients; the third patient died of disease progression with persistent hepatitis. The two patients with Grade 3 hepatitis that resolved restarted nivolumab and, in one patient, Grade 3 immune-mediated hepatitis recurred resulting in permanent discontinuation of nivolumab.

- **Immune-mediated nephritis and renal dysfunction. Creatinine greater than 1.5 and up to 6 times ULN or greater than 1.5 times baseline**

In Trial 1, there was an increased incidence of elevated creatinine in the nivolumab-treated group as compared to the chemotherapy-treated group (13% vs. 9%). Grade 2 or 3 immune-mediated nephritis or renal dysfunction (defined as > Grade 2 increased creatinine, requirement for corticosteroids, and no clear alternate etiology) occurred in 0.7% (2/268) of patients at 3.5 and 6 months after nivolumab initiation, respectively. Nivolumab was permanently discontinued in both patients; both received high-dose corticosteroids (at least 40 mg prednisone equivalents). Immune-mediated nephritis resolved and did not recur with continuation of corticosteroids in one patient. Renal dysfunction was ongoing in one patient.

- **Immune-mediated hypothyroidism or hyperthyroidism**

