6.2. ABI-009 Dose Modification and Stopping Rules

6.2.1. Dosage Adjustments, Delays, Rules for Withholding or Restarting, Permanent Discontinuation

If, treatment cannot be administered on the planned visit date, ABI-009 may be administered +/- 2 days from the scheduled date. Prior to ABI-009 administration on Day 1 of each cycle, patients must meet the following hematological requirements:

- ANC $\geq 1.5 \times 10^9/L$
- Platelet count $\geq 100 \times 10^9/L$
- Hemoglobin $\geq 9 \text{ g/dL}$

The treatment will be on hold up to 14 days until the patient has fulfilled these criteria.

If a Grade 4 hematologic toxicity occurs, the dose of ABI-009 is held until toxicity resolves to Grade 1 or less. The dose of ABI-009 is then modified according to the dose modification section. If a Grade 3 non-hematologic toxicity occurs, both nivolumab and ABI-009 are withheld until toxicity resolves to Grade 1 or less. The dose of ABI-009 is then modified according to the dose modification section. Nivolumab has no dose modification.

The maximum delay between a missed scheduled dose and the next one (whichever dose was missed) should not be longer than 14 days. Approval from the Medical Monitor is required to restart study treatment after ≥ 21 days of interruption.

During the Phase 2 part of the study, doses of ABI-009 will be reduced for hematologic and other toxicities. Two levels of dose modifications are permitted according to the criteria below. If MTD is determined to be 56 mg/m², dose reductions will occur sequentially (45 mg/m² and 30 mg/m²), there should be no direct reduction by two dose

levels. If a toxicity requiring dose modification occurs following the second dose reduction of ABI-009, further treatment should be discontinued. Dose adjustments are to be made according to the system showing the greatest degree of toxicity. Toxicities will be graded using the NCI CTCAE Version 4.03.

Guidelines for dose modifications and interruptions for management of common toxicities associated with the study treatment(s) are provided in this section:

- General guidelines for clinically significant toxicities related to study treatment

And

- Specific guidelines for adverse events of special interest, which are events that have been observed with higher frequency or severity.

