6.3. Nivolumab Dose Modification and Stopping Rules

6.3.1. Dose Modification and Stopping Rules

Nivolumab (Opdivo®); see product information at www.accessdata.fda.gov

Withhold nivolumab for any of the following:

- Immune-mediated Grade 2 pneumonitis**

Monitor patients for signs and symptoms of pneumonitis. Administer corticosteroids at a dose of 1 to 2 mg/kg/day prednisone equivalents for Grade 2 or greater pneumonitis, followed by corticosteroid taper. Permanently discontinue nivolumab for severe (Grade 3) or life-threatening (Grade 4) pneumonitis and withhold nivolumab until resolution for moderate (Grade 2) pneumonitis

- Immune-mediated Grade 2-3 colitis**

Monitor patients for immune-mediated colitis. Administer corticosteroids at a dose of 1 to 2 mg/kg/day prednisone equivalents followed by corticosteroid taper for severe (Grade 3) or life-threatening (Grade 4) colitis. Administer corticosteroids at a dose of 0.5 to 1 mg/kg/day prednisone equivalents followed by corticosteroid taper for moderate (Grade 2) colitis of more than 5 days duration; if worsening or no improvement occurs despite initiation of corticosteroids, increase dose to 1 to 2 mg/kg/day prednisone equivalents. Withhold nivolumab for Grade 2 or 3 immune-mediated colitis. Permanently discontinue nivolumab for Grade 4 colitis or for recurrent colitis upon restarting nivolumab.

- Immune-mediated hepatitis.** Aspartate aminotransferase (AST) or alanine aminotransferase (ALT) greater than 3 and up to 5 times upper limit of normal (ULN) or total bilirubin greater than 1.5 and up to 3 times ULN

Monitor patients for abnormal liver tests prior to and periodically during treatment. Administer corticosteroids at a dose of 1 to 2 mg/kg/day prednisone equivalents for Grade 2 or greater transaminase elevations, with or without concomitant elevation in total bilirubin. Withhold nivolumab for moderate (Grade 2) and permanently discontinue nivolumab for severe (Grade 3) or life-threatening (Grade 4) immune-mediated hepatitis

- Immune-mediated nephritis and renal dysfunction. Creatinine greater than 1.5 and up to 6 times ULN or greater than 1.5 times baseline**

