6.3.2. Dosage Adjustments, Delays, Rules for Withholding or Restarting, Permanent Discontinuation

Resume nivolumab in patients whose adverse reactions recover to Grade 0-1.

Permanently discontinue nivolumab for any of the following:

- Any life-threatening or Grade 4 adverse reaction
- Grade 3 or 4 pneumonitis
- Grade 4 colitis
- AST or ALT greater than 5 times ULN or total bilirubin greater than 3 times ULN
- Creatinine greater than 6 times ULN
- Any severe or Grade 3 treatment-related adverse reaction that recurs
- Inability to reduce corticosteroid dose to 10 mg or less of prednisone or equivalent per day within 12 weeks
- Persistent Grade 2 or 3 treatment-related adverse reactions that do not recover to Grade 0-1 within 12 weeks after last dose of nivolumab

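### Section 6.3.2 permanently stops nivolumab at AST/ALT above 5 x ULN or bilirubin above 3 x ULN, but the hepatic appendix footnote and the general Grade 3 rule in Section 6.2.1 allow hold-and-resume, and no visible text says which prevails

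*Combined protocol and SAP*

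**What the plan says.** Section 6.3.2 lists the events after which nivolumab is stopped for good. One entry is "AST or ALT greater than 5 times ULN or total bilirubin greater than 3 times ULN". It has no upper bound and no exception, and it is not restricted to immune-mediated cases.

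Section 6.3.1 is consistent with this. For transaminases, its hepatitis entry in the list of reasons to withhold nivolumab gives the range "greater than 3 and up to 5 times upper limit of normal (ULN) or total bilirubin greater than 1.5 and up to 3 times" the same limit. By grade it says: "Withhold nivolumab for moderate (Grade 2) and permanently discontinue nivolumab for severe (Grade 3) or life-threatening (Grade 4) immune-mediated hepatitis".

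Two other texts allow a hold followed by restart:

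- The hepatic algorithm in the nivolumab appendix has the footnote "I-O therapy may be delayed rather than discontinued if AST/ALT ≤ 8 x ULN or T.bili ≤ 5 x ULN".
- Section 6.2.1 says that for Grade 3 non-hematologic toxicity both drugs are held until Grade 1 or lower. After that only the ABI-009 dose is adjusted.

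Section 6.3 does not refer to the appendix, the visible appendix text does not refer to Section 6.3, and nothing visible ranks Section 6.2.1 against either. The hepatic flowchart is a figure missing from the available text, so the box that carries the footnote's asterisk cannot be read.

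**The concern.** This is a safety stop, and the protocol gives more than one answer for the same laboratory value. A patient with ALT of 6 x ULN must never receive nivolumab again under Section 6.3.2, yet may restart under the footnote. The same patient may also restart under Section 6.2.1 if the event is Grade 3.

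The decision has some weight in this trial. Section 7.6 gives dexamethasone from Cycle 2 partly to prevent hepatitis on the combination. Section 2.3 makes Grade 3 or worse hepatitis a DLT. Section 3.2 admits patients whose AST/ALT is up to 5 x ULN because of liver metastases, and hepatocellular carcinoma is an eligible diagnosis. For some patients a small rise is enough to reach the disputed range.

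**Working it through.** No statistical figure in the plan depends on this point, so the main check sets the limits side by side.

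| Text | AST/ALT | Total bilirubin | Action on nivolumab |
|---|---|---|---|
| Section 6.3.1 | >3 to 5 x ULN | >1.5 to 3 x ULN | Withhold |
| Section 6.3.2 | >5 x ULN | >3 x ULN | Permanent stop |
| Appendix footnote | ≤8 x ULN | ≤5 x ULN | Delay allowed instead of stop |
| Section 6.2.1 | by grade: Grade 3 | by grade: Grade 3 | Withhold until Grade 1 or less |

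**Step 1: overlap of Section 6.3.2 and the footnote.**

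- AST/ALT: (>5) and (≤8) gives above 5 and up to 8 x ULN.
- Bilirubin: (>3) and (≤5) gives above 3 and up to 5 x ULN.

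This is the minimum conflict. The footnote joins its two limits with 'or'. Read literally, one limit is enough: AST/ALT of 12 x ULN with bilirubin of 2 x ULN would qualify for delay, because the bilirubin limit is met. On that reading the conflict is wider.

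**Step 2: overlap with Section 6.2.1.** Section 6.3.1 pairs withholding with Grade 2 and permanent stop with Grade 3 or 4. Its withhold range ends at 5 x ULN for AST/ALT and 3 x ULN for bilirubin, exactly where Section 6.3.2 begins. Grade 3 hepatitis is therefore a permanent stop under Section 6.3.1 and a hold-and-resume event under the general rule in Section 6.2.1. This conflict lies in the protocol body and does not depend on the appendix.

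**Step 3: what still limits a restart.**

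- Section 6.3.2: "Resume nivolumab in patients whose adverse reactions recover to Grade 0-1".
- Section 6.2.1: no more than 14 days between a missed dose and the next; and "Approval from the Medical Monitor is required to restart study treatment after" 21 or more days of interruption.
- Section 6.3.2: permanent stop if a Grade 2 or 3 related reaction has not recovered to Grade 0-1 within 12 weeks of the last nivolumab dose, or if steroids cannot be reduced to 10 mg or less of prednisone per day within 12 weeks.
- Section 6.3.2: permanent stop for "Any severe or Grade 3 treatment-related adverse reaction that recurs".

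The last of these acts only after a second event. The others act before or without one.

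**Step 4: rough frequency.** The documents do not say how many patients will fall in the range. The nearest figure is in Section 1.3.3, where immune-mediated hepatitis "occurred in 1.1% (3/268) of patients receiving nivolumab: two patients with Grade 3 and one patient with Grade 2 hepatitis".

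- Grade 3 rate: 2/268 = 0.00746, or 0.75%. Exact (Clopper-Pearson) 95% CI: 0.00091 to 0.02670.
- Expected patients if that rate applied: 0.00746 × 40 = 0.30 and 0.00746 × 50 = 0.37.
- Range over the CI: 0.00091 × 40 = 0.04 to 0.02670 × 50 = 1.3.

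Trial 1 gave nivolumab alone every 2 weeks in melanoma, its AST/ALT levels are not reported, and the Section 6.3.2 limit covers a rise of any cause. The true frequency here could be higher or lower.

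**The case against.** The strongest case on the other side has five parts.

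- **The footnote is permissive.** Always stopping complies with both the footnote and Section 6.3.2. A reader might infer that the texts cannot both be followed; that is too strong. What stands is that anyone who uses the written permission breaches Section 6.3.2.
- **The flowchart is missing.** The asterisked box and any conditions in it are unknown. This limits how exactly the footnote can be reworded. It does not remove the conflict, because the footnote states its own limits and offers relief from a discontinuation.
- **The trial has one center (Section 5.1).** A reader might infer inconsistent handling between sites; that cannot arise here. Inconsistent handling between patients at that center still can.
- **The consequence is small.** The expected count is below one patient, and the limits on restart in Sections 6.2.1 and 6.3.2 are real. A reader might infer that the footnote opens the way to unguarded rechallenge; it does not. This argues for moderate priority, not for leaving the contradiction in place.
- **The stricter limit is partly a choice.** The documents do not show which limit the sponsor intended, and patients with liver metastases pay the price of the stricter one. That is fair. But Sections 6.3.1 and 6.3.2 agree with each other, so aligning to them is the smaller and safer change.

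**Conclusion.** The contradiction is real and should be corrected. Section 6.3.2, supported by Section 6.3.1 for Grade 3-4 immune-mediated hepatitis, requires a permanent stop where the appendix footnote and Section 6.2.1 each allow hold-and-resume. The minimum conflict with the footnote is AST/ALT above 5 and up to 8 x ULN and bilirubin above 3 and up to 5 x ULN, wider if 'or' is taken literally. The case is likely rare: 0.3 to 0.4 expected patients among 40 to 50, with 0.04 to 1.3 over the confidence interval, assuming the Trial 1 rate carries over.

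Two stronger readings are not supported. A reader might infer that dose finding is affected. It is not: Grade 3 or worse hepatitis is a DLT under Section 2.3 whether nivolumab is then stopped or delayed, so DLT counting and the MTD do not change. A reader might also take the Trial 1 rechallenge experience in Section 1.3.3 as a recurrence risk: two patients restarted after Grade 3 hepatitis and it recurred in one. Two patients establish no rate, and without their AST/ALT levels they cannot be placed in the disputed range.

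**What to change.** 1. Delete the hepatic footnote, or limit it to the withhold range already in Section 6.3.1: 'Nivolumab may be delayed instead of stopped only when AST/ALT is at most 5 x ULN and total bilirubin is at most 3 x ULN.' State in the change record that 'or' becomes 'and'. Check the flowchart first: if the asterisk sits on a box for values above 5 x ULN, the limited footnote could never apply and deletion is the better option.
2. Add to Section 6.3.2: 'For nivolumab, the hepatic limits in this section prevail over the hepatic appendix footnote and over the general Grade 3 rule in Section 6.2.1.'
3. Leave as it is the appendix instruction to treat the cause and continue therapy when the cause is non-inflammatory. Section 6.3.2 is not limited to immune-mediated rises, so whether it should override that instruction too is a clinical decision for the sponsor.

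The cost is one footnote and one sentence, with no extra patients, visits or CRF items. The downside is that some patients, mainly those who enter with liver metastases and AST/ALT up to 5 x ULN, stop nivolumab after a small rise. Section 6.3.2 already requires this. If the sponsor wants to spare them, a limit relative to baseline belongs in Section 6.3.2.
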